**Subject inclusion criteria:**

- Adults ≥18 years of age
- Diagnosis of T1DM for > 1 year
- On MDI using a basal-bolus insulin regime or continuous subcutaneous insulin infusion (insulin pump)
- Structured education
- HbA1c ≥ 48mmol/mol and ≤ 86mmol/mol
- No severe hypoglycaemia (defined as needing 3rd party assistance) in previous year

**Subject exclusion criteria:**

- Recurrent severe hypoglycaemia
- Pregnant or planning pregnancy
- Breastfeeding
- Enrolled in other clinical trials
- Have active malignancy or under investigation for malignancy
- Addison's Disease
- Gastroparesis
- Autonomic neuropathy

- Concomitant use of GLP-1 analogues, sodium-glucose co-transporter-2 (SGLT2) inhibitors and gliptins
- Visual impairment
- Reduced manual dexterity

**Subject withdrawal criteria:**

- Loss of capacity to give informed consent
- Cessation of MDI of insulin as usual care for T1DM
- Recurrent severe hypoglycaemia
- Terminal illness

Withdrawal will be immediate and subjects will be followed up in the appropriate out-patient diabetes clinic within 4 weeks of withdrawal

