**Randomisation**

Subjects who fit the inclusion criteria will be randomized to either ABC4D (intervention group) or standard care (control group) in a 1:1 ratio

Standard care is defined as the bolus wizard within insulin pumps, bolus calculator in glucose meter or the ABC4D app as a standard bolus calculator (without CBR adaptation)

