### **Clinical review at 1 month, 3 months and 6 months:**

*Review at 1 month (coincides with visit 4):*

- Review of subject's diabetes control including insulin requirements, incidence of hypoglycaemia, exercise, driving etc.

*Review at 3 months (coincides with visit 6):*

- Review of subject's diabetes control including insulin requirements, incidence of hypoglycaemia, exercise, driving etc.
- Random venous blood taken for HbA1c
- Weight (kg)

*Review at 6 months (coincides with visit 8):*

- Review of subject's diabetes control including insulin requirements, incidence of hypoglycaemia, exercise, driving etc.
- Random venous blood taken for HbA1c
- Weight (kg)
- PAID score, DQOL and DTSQ questionnaires to be completed

Usual care will be maintained for diabetes throughout the study. No concomitant medical therapies are contra-indicated, except GLP-1 analogues, SGLT2 inhibitors and gliptins. Support will be offered to any participants who have concerns about their diabetes management.

Subjects in the intervention group using the ABC4D will have the opportunity to call a physician for medical support and an engineer for technical support 24 hours a day throughout the study.

**Statistics** This is a randomised study with an intervention group and a control group. Outcomes from the study are absolutes as described above. 142 subjects with T1DM, are required to demonstrate an HbA1c difference of 0.6% with  $\alpha$  of 0.05 and 90% power (two-tailed). We aim to screen n=160 and randomise n=80 in each group. This power calculation is based on using a population mean HbA1c of 7.9% with a standard deviation of 1.1.

The sample size is comparable to other technology transfer studies, is a realistic number for recruitment and provides robust clinical validation and safety date of a new technology.

[figure not shown]
Missing, unused, and spurious data will be assessed on an individual basis and may be ignored, withdrawn or the visit may be removed from the analysis with appropriate justification adjudicated by the Principal Investigator.

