**Secondary outcomes:**

HbA1c at 3 months  
Post-prandial AUC at 4 hours and 6 hours  
Post-prandial AUC (<3.9) at 4 hours and 6 hours  
Episodes of hypoglycaemia within 4- and 6-hours post-prandially  
% time in target glucose (3.9-10mmol/l)  
% time in hypo- (<3.9mmol/l) and hyperglycaemia (>10mmol/l)  
Glycaemic risk: LBGI and HBGI  
Glycaemic variability: MAGE and CONGA-2  
Change in weight (kg)  
Number achieving target HbA1c (≤ 53 mmol/mol)  
24-hours insulin dose requirements  
PAID score questionnaire  
DQOL questionnaire  
DTSQ Questionnaire  
Acceptability questionnaire (non-validated)

These are validated, published metrics.

**Timescale:** Each subject will be in the study for 6 months. It is anticipated that it will take 15 months to complete the 4th phase.

**Population:** 142 subjects with T1DM, are required to demonstrate an HbA1c difference of 0.6% with  $\alpha$  of 0.05 and 90% power (two-tailed). We aim to screen n=180 and randomise n=90 in each group. This power calculation is based on using a population mean HbA1c of 7.9% with a standard deviation of 1.1.

The first 25 participants will be randomised to either the ABC4D running in semi-automatic mode (where the revisions are done using a semi-automatic process-see page 23) or a standard bolus calculator. The remaining participants will be randomised to either the fully automated ABC4D (where revisions are fully automated) or a standard bolus calculator. Screening 180 participants will ensure that at least 142 participants are included to enable demonstration of a significant difference between the fully automated ABC4D system and a standard bolus calculator.

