### ABC4D case base revision and adaptation

The ABC4D case base will be revised every two weeks throughout the study and this will be a semi-automatic process for the first 25 participants entered into the study if allocated to the intervention group. For the remaining 155 participants, if allocated to the intervention group, the revisions will be fully automated requiring minimal manual input. The adaptation summary will be approved and the case-base updated by the study team. This provides remote supervision and prevents any potential system faults despite safety measures. The subjects will not need to attend the clinical research unit for the ABC4D revisions.

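### Phases 3 and 4 admit pump users but keep the MDI-only withdrawal rule, so moving from MDI to a pump means withdrawal and the 6-month HbA1c may be lost

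*Combined protocol and SAP*

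**What the plan says.** The inclusion criteria of Phases 3 and 4 accept either delivery mode: "On MDI using a basal-bolus insulin regime or continuous subcutaneous insulin infusion (insulin pump". The Randomisation sections of both phases also place the pump's own calculator in the control condition: "Standard care is defined as the bolus wizard within insulin pumps, bolus calculator in glucose meter".

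The Subject withdrawal criteria of the same two phases list "Cessation of MDI of insulin as usual care for T1DM". Nothing corresponds to it for stopping a pump. The consequence is the same for every criterion on the list: "Withdrawal will be immediate and subjects will be followed up in the appropriate out-patient diabetes clinic within 4 weeks of withdrawal". Study visits and HbA1c after withdrawal are not mentioned.

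The primary outcome in both phases is HbA1c at 6 months. On missing data, the Statistics paragraphs say: "Missing, unused, and spurious data will be assessed on an individual basis and may be ignored, withdrawn", with the Principal Investigator adjudicating. No analysis population is defined.

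The Consent paragraph under Regulatory Issues applies to all four phases. It keeps a participant whose clinician chooses another treatment in the study for follow-up and analysis, and it describes a participant's own withdrawal as withdrawal from protocol treatment.

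**The concern.** The criterion is identical in all four phases. In Phases 1 and 2, where only MDI users were eligible, it made sense. In Phases 3 and 4 eligibility was widened and the criterion was not, so it looks like a drafting carry-over.

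Followed literally, it removes a randomised participant for adopting a delivery mode that the trial admits, and it does so in one direction only. It says nothing usable about people already on a pump at entry.

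The statistical stake is the primary outcome. If a site applies the rule and ends study visits, the 6-month HbA1c is lost after randomisation, and only among MDI users. Both phases are open-label, so a decision to change delivery mode could be influenced by the allocated arm. The missing value would then be handled case by case, with no rule fixed in advance.

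**Working it through.** **The text, phase by phase**

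| Phase | Eligible at entry | Withdrawal on stopping MDI | Withdrawal on stopping pump |
|---|---|---|---|
| 1 | MDI | Yes | Not applicable |
| 2 | MDI | Yes | Not applicable |
| 3 | MDI or pump | Yes, same wording | None |
| 4 | MDI or pump | Yes, same wording | None |

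In Phases 3 and 4, a move from MDI to pump therefore triggers withdrawal and a move from pump to MDI does not.

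**The plan's own sample size**

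Inputs (Population and Statistics, Phases 3 and 4): difference 0.6, SD 1.1, two-sided alpha 0.05, power 90%.

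n per arm = 2 × SD² × (z₀.₉₇₅ + z₀.₉₀)² / difference² = 2 × 1.21 × (1.960 + 1.282)² / 0.36 = 70.6, rounded up to 71. The total is 142, as stated, with power 90.1% (normal approximation).

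**Participants available**

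- Phase 3: 160 randomised. Margin over 142 = 18, and 18/160 = 11.25%.
- Phase 4: the plan links the 142 to one comparison, so that "at least 142 participants are included to enable demonstration of a significant difference between the fully automated ABC4D system" and a standard calculator can be shown. The first 25 participants use the semi-automatic version if allocated to intervention, which leaves 180 − 25 = 155: "For the remaining 155 participants, if allocated to the intervention group, the revisions will be fully automated requiring minimal manual input". Margin = 155 − 142 = 13, and 13/155 = 8.4%.

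The Phase 4 Statistics paragraph still gives 160 where the Population paragraph gives 180. That is a separate conflict; 180 is used here.

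**Assumptions not in the documents**

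- MDI share of participants: 50% to 100%.
- MDI users moving to a pump within 6 months: 2% to 10%.
- Every such move loses the 6-month HbA1c, so the share lost is p = 0.5 × 0.02 = 1% to 1.0 × 0.10 = 10%.
- Mean 6-month HbA1c of those lost minus that of those remaining (d): 0.55 to 1.1 points, which is 0.5 to 1 SD.

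Power = Φ(0.6 / (1.1 × √(1/n₁ + 1/n₂)) − 1.96).

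**Scenario A: equal and similar loss in both arms.** Bias is near zero.

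| Comparison | No loss | 1% lost | 10% lost |
|---|---|---|---|
| Phase 3 | 160, 93.2% | 158.4, 93.0% | 144, 90.5% |
| Phase 4, fully automated | 155, 92.4% | 153.45, 92.2% | 139.5, 89.6% |

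Phase 3 stays above 142 across the assumed range. Phase 4 falls below 142 once loss passes 8.4%.

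**Scenario B: all loss in one arm, completers only analysed**

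- Phase 3: one arm falls from 80 to between 79.2 and 72. Total 159.2 to 152, power 93.1% to 91.9%.
- Phase 4: one arm falls from 77.5 to between 76.7 and 69.75. Total 154.2 to 147.25, power 92.3% to 91.1%.

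The completers' mean in that arm is off by p × d:

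- 0.01 × 0.55 = 0.0055, or 0.9% of 0.6
- 0.025 × 0.55 = 0.014, or 2.3% (50% MDI, 5% switching, 0.5 SD)
- 0.05 × 1.1 = 0.055, or 9.2%
- 0.10 × 1.1 = 0.11, or 18.3%

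**The case against.** The best reply is that this is a wording slip which nobody would apply literally, and that the Consent paragraph already deals with the consequence. That paragraph is the only text on follow-up for analysis, and it favours keeping people in. The withdrawal lists do not say that data collection stops. This carries weight: it makes loss of the outcome a possibility and no more. But the paragraph does not refer to the withdrawal criteria or override the immediate withdrawal they require, so a site could follow either text.

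Second, the rule is the same in both arms, so its asymmetry between delivery modes does not by itself bias the comparison. That is correct. A difference between arms needs switching to depend on allocation; open-label conduct allows this, but the documents give no evidence of it.

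Third, silence about HbA1c after withdrawal affects all four criteria. That is also correct. What is particular to this one is that it withdraws people for moving to a mode the trial accepts.

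Fourth, the larger figures are extreme. The 0.11 bias needs every participant on MDI, 10% switching, a full-SD difference and all loss in one arm. The Phase 4 shortfall needs loss above 8.4%, hence at least 84% on MDI even at 10% switching. The plan also says "Usual care will be maintained for diabetes throughout the study", which suggests that switches were not expected to be common. These points support a low rating; they leave the inconsistency in place.

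**Conclusion.** The concern holds and is minor. As written, the withdrawal rule in Phases 3 and 4 conflicts with their eligibility criteria and can remove randomised participants in one direction only. Whether their 6-month HbA1c is kept is not settled by the text.

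The size cannot be derived from the documents, which give neither the MDI share nor the switching rate. Under the assumptions above, the worst power is 89.6% against a planned 90%. Bias is near zero if loss is balanced and similar in the two arms; the moderate one-arm case gives about 0.014 HbA1c points and the extreme one 0.11. The likely effect is small. The finding on the text is firm; its practical effect is uncertain.

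**What to change.** In the Subject withdrawal criteria of Phases 3 and 4:

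- Replace the MDI criterion with one neutral between delivery modes, such as cessation of both MDI and pump therapy. If the calculator must stop when delivery mode changes, make that discontinuation of the intervention only, and apply it in both directions.
- Add one sentence. Participants who meet any withdrawal criterion, or whose change of delivery mode stops the calculator, discontinue the intervention. Subject to consent and capacity, they still have the scheduled 3- and 6-month HbA1c and are analysed in the arm to which they were randomised.

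This agrees with the Consent paragraph and closes the same gap for the other three criteria. The cost is wording in two places, plus attendance at HbA1c visits already in the schedule for the few people who would otherwise have left.

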**Recruitment**

Recruiting will be undertaken in the diabetes clinics at Imperial College Healthcare NHS Trust, from registered research databases and from interested subjects who contact us. Participant information sheets will be given to potential subjects and, after a minimum of 48 hours and following any questions, informed consent will be taken.

*Subjects who have already participated in phase 1 and/or 2 of the study can also be recruited for phase 3 and they will be re-consented. These subjects will not need re-screening, however they may need to repeat 1 week of CGM using iPRO2 for initializing of the ABC4D at the start of the Phase 3 study, this is at the discretion of the Principal Investigator.*

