**Subject inclusion criteria:**

- Adults ≥18 years of age
- Diagnosis of T1DM for > 1 year
- On MDI using a basal-bolus insulin regime
- Structured education in previous 3 years
- HbA1c ≤ 86mmol/mol
- No severe hypoglycaemia (defined as needing 3rd party assistance) in previous year

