**Subject exclusion criteria:**

- Recurrent severe hypoglycaemia
- Pregnant or planning pregnancy
- Breastfeeding
- Enrolled in other clinical trials
- Have active malignancy or under investigation for malignancy
- Addison's Disease
- Gastroparesis
- Autonomic neuropathy
- Concomitant use of GLP-1 analogues and gliptins
- Visual impairment
- Reduced manual dexterity

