**Visit 1: Screening**

- Attend the clinical research unit
- Routine clinical examination
- ECG
- Non-fasting venous blood taken for HbA1c, creatinine, lipids.
- Urine for albumin/creatinine ratio
- Urine pregnancy test in female subjects of childbearing age
- CHO counting and hypoglycaemia education revision by a qualified health care professional.
- The basal insulin dose will be reviewed and adjusted if needed.
- Questionnaires to be completed
- Continuous glucose monitor (CGM retrospective/blinded iPro2, Medtronic or Dexcom) placed in the anterior abdominal wall according to manufacturer's instructions. CGM sensor to be worn for 6-7 continuous days.
- Instructions to subjects to ensure:
  - Capillary blood glucose measurements fasting, pre-meals, post-meals and pre-bed.
  - Food diaries and physical activity record to be kept for 6 days

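### Phase 3 waives re-screening for Phase 1/2 participants although its eligibility limits are tighter: they have no scheduled current pregnancy test or baseline questionnaires, and a current HbA1c is only implied

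*Combined protocol and SAP*

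**What the plan says.** - **Waiver.** Phase 3, Recruitment: people from Phase 1 and/or 2 can be "recruited for phase 3 and they will be re-consented. These subjects will not need re-screening". The only procedure it may ask of them is another week of CGM, at the Principal Investigator's discretion.
- **HbA1c limits.** Phase 3 inclusion criteria: "HbA1c ≥ 48mmol/mol and ≤ 86mmol/mol". Phase 2 set only an upper limit, "HbA1c ≤ 86mmol/mol", and Phase 1 did the same.
- **Drug exclusion.** Phase 3: "Concomitant use of GLP-1 analogues, sodium-glucose co-transporter-2 (SGLT2) inhibitors and gliptins". Phase 2, like Phase 1: "Concomitant use of GLP-1 analogues and gliptins".
- **Criteria that change with time.** Phase 3 excludes "Pregnant or planning pregnancy" and requires a year free of severe hypoglycaemia.
- **Where these are measured.** Phase 3, Visit 1: Screening lists venous HbA1c, "Urine pregnancy test in female subjects of childbearing age" and "Questionnaires to be completed". Visit 2 lists none of these in either arm. HbA1c next appears at 3 months and questionnaires at 6 months. The overview table for the intervention group marks the pregnancy test at Visit 1 only.
- **Passages pointing the other way.** Phase 3, Randomisation allocates those who meet the inclusion criteria. Potential risks and benefits says that a venous blood sample is taken as each phase begins, without naming HbA1c.
- **Phase 4.** The same HbA1c limits and SGLT2 exclusion apply, and its Recruitment paragraph requires returning Phase 1/2 participants to be screened again.

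**The concern.** A participant can have passed Phase 1 or Phase 2 screening and still fail Phase 3: by an HbA1c under the new lower limit, by taking an SGLT2 inhibitor, or because pregnancy or severe hypoglycaemia has occurred since. The waiver sends such a person into a randomised phase without the visit at which those facts are established. At stake are three things:

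- eligibility, and in the case of pregnancy participant safety;
- an HbA1c limit that may be judged against an old value;
- PAID, DQOL and DTSQ scores at 6 months with nothing recorded before allocation.

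The plan also treats the same people in opposite ways in Phases 3 and 4, and gives no reason.

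**Working it through.** **1. What the waiver covers.** The CGM week is itself an item of Phase 3 Visit 1. Naming it as the one thing that may be repeated implies that the rest of Visit 1 is skipped. No other passage schedules the Visit 1 tests for these people.

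**2. Item by item, for a returning participant.**

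| Item | Checked at earlier screening? | Scheduled before Phase 3 allocation if Visit 1 is skipped? |
|---|---|---|
| Lower HbA1c limit | HbA1c measured, limit not applied | Implied only (Randomisation; blood test at start of phase) |
| SGLT2 inhibitor | Not an exclusion | Not itemised; a medication question would settle it |
| Pregnancy | Yes, at that date | No |
| Severe hypoglycaemia in past year | Yes, for a different year | Not itemised |
| PAID, DQOL, DTSQ | No; Phases 1 and 2 list only an acceptability questionnaire | No |

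**3. How many people.** Phase 1 plans 6 and Phase 2 plans 20, and Phase 1 participants may also join Phase 2.
- Distinct people: 20 (all six overlap) to 6 + 20 = 26 (none overlap).
- Share of the 160 planned: 20/160 = 12.5%; 26/160 = 16.3%.
- Expected per arm under 1:1 allocation: 10 to 13 of 80.
- The return rate is not given. At 0% the number is 0; at an assumed 50% it is 10 to 13 (6.3% to 8.1%); at 100% it is 20 to 26.

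**4. How old the earlier screening can be.** Planned durations are 2, 4 and 15 months for Phases 1, 2 and 3, with 6 months per Phase 3 participant.
- Last Phase 3 entry: 15 − 6 = month 9.
- Screened at the start of Phase 2: 4 + 9 = 13 months.
- Screened at the start of Phase 1: 2 + 4 + 9 = 15 months. The Phase 2 Recruitment paragraph has the same waiver, so a Phase 1 screening can carry through both transitions.
- Shortest case, screened in Phase 2 and completing it: Visit 2 at day 7 plus Visit 7 at 35 days later = day 42, and one more sensor week = day 49, so 6 to 7 weeks.

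These assume no gap between phases; any gap adds its own length.

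**5. Scale against the sample size.** The plan's figure reproduces: n per arm = 2 × (1.960 + 1.282)² × 1.1² / 0.6² = 70.6, rounded up to 71, or 142 in total. By the normal approximation, power is 93.2% with 160. If every returning participant were left out of an analysis, 160 − 20 = 140 or 160 − 26 = 134 would remain, with power 89.7% or 88.4%. This is an outer bound with no other losses. Nothing in the plan calls for that exclusion.

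**The case against.** The strongest reply is that the exclusion criteria bind whatever Recruitment says: a pregnant participant is ineligible with or without a test, re-consent is kept, and staff would check. The first part stands. What is missing is a scheduled test, not the exclusion. But a written waiver permits staff not to test, and the protocol is where consistent handling of new and returning participants should be set.

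The HbA1c part is softened by the Randomisation and Potential risks passages, which together imply a current value. That also stands, so the fault there is an unreconciled conflict. The SGLT2 point is minor, because the usual-care text bars these drugs during Phase 3.

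Three stronger readings are tempting, and the documents do not support them:

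- **That the primary result is biased.** The Phase 3 primary outcome is HbA1c at 6 months, compared between randomised arms. It needs no baseline, and returning participants are allocated 1:1 like everyone else.
- **That change in HbA1c is undermined.** Trial Objectives words the Phase 3 primary outcome as a change, but the Phase 3 section does not. That mismatch is a separate matter which the waiver did not create, and every returner has some earlier HbA1c.
- **That the questionnaire outcomes are lost.** They are listed as plain scores, Phase 3 Statistics calls the outcomes absolutes, and no baseline-adjusted analysis is specified. The 6-month comparison can be made without a baseline.

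The 13 and 15 months are extremes, pairing the earliest screening with the latest entry, and should not be read as typical.

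**Conclusion.** The concern holds as a conflict between a stated rule and the plan's own eligibility criteria. It is limited in reach: at most 20 to 26 people, possibly none. For them no current pregnancy test is scheduled, a current HbA1c is implied but not stated, and no baseline PAID, DQOL or DTSQ is scheduled or available from earlier phases. The questionnaire gap costs baseline description and perhaps some precision. The between-arm primary comparison is unaffected.

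This rests on reading the waiver as covering all of Visit 1, on planned rather than actual enrolment in Phases 1 and 2, and, for the screening ages, on the planned durations with no gaps. It is worth correcting for eligibility and participant safety.

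**What to change.** In the Phase 3 Recruitment paragraph, replace the waiver with the rule in the Phase 4 Recruitment paragraph: returning participants are both screened and consented again. The Phase 3 eligibility check and the Visit 1 HbA1c, pregnancy test and questionnaires are then completed before randomisation. This brings Recruitment into line with the Phase 3 inclusion and exclusion criteria, the Randomisation section and the statement about blood tests at the start of each phase.

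If the CGM week is to stay at the Principal Investigator's discretion, say so as an explicit exception and reconcile it with Visit 2. In both arms Visit 2 starts by removing a sensor and recalculates ISF and ICR after CGM; in the intervention arm it also builds the initial case base from CGM data and the diary. Those steps have no input for someone who wore no sensor.

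The cost is a few lines of text and one existing visit for at most 26 people. No new procedure is needed.
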